#### 4.5 Safety

#### 4.5.1 Adverse Events

All AEs that occur during the study or continue after enrollment into this study will be recorded and classified on the basis of Medical Dictionary for Regulatory Activities (MedDRA) terminology version 18.1. Adverse events ongoing at end of the pivotal study will be carried forward to this study, will not be considered treatment-emergent for this study, and will be summarized separately by SOC, PT, and relatedness. Treatment-emergent AEs (TEAEs) will be defined as AEs reported on or after the first day of enrollment in this long term safety study.

All information pertaining to an AE noted during the study will be listed by subject, detailing verbatim term given by the Investigator or designee, preferred term, system organ class (SOC), onset date, resolution date, severity, seriousness, action taken, outcome, and drug relatedness. The event onset will also be shown relative (in number of days) to date of first dose in this study.

Treatment-emergent AEs will be summarized by the number of subjects reporting a TEAE, SOC, preferred term, severity, relationship to study drug (causality), and seriousness. When summarizing AEs by severity and relationship, each subject will be counted only once, within a system organ class or a preferred term, by using the event with the highest severity and greatest relationship within each classification.

Serious AEs will be summarized by severity, and relationship to study drug, and individual SAEs will be listed by subject. In addition, a list of subjects who prematurely discontinue study drug due to an AE, had AEs leading to treatment modification, and AEs that resulted in death will be provided.

Adverse events will also be summarized by windows of duration of exposure to study drug to determine if there is a safety signal due to duration of exposure. The windows of exposure will include but are not limited to: 1) within the first 24 hours (i.e. Day 1 of the LTS study), 2) up to 1 month (i.e. 2-30 days), 3) up to 3 months (i.e. 31-90 days), 4) up to 6 months (i.e. 91-180 days) and 5) up to 12 months (i.e. 181-365 days).

Adverse event incidence will also be summarized by the extent of exposure categories (in grams) as described in section 4.4.

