4.3 SAFETY ASSESSMENTS

Adverse events will be collected beginning with the Baseline Visit for this study. Adverse events that began during NI-AC301 or NI-AC302 that are ongoing at the conclusion of either study will be reported as AEs at Baseline in this long-term safety study (NI-AC303) and followed. The physical exam, vital signs and pregnancy test results from the Week 12 visit of NI-AC301 or NI-AC302 will be used as the subject's Baseline assessments for this long term safety study and be collected during the study.

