6. EVALUATION OF ADVERSE EVENTS

6.1 DEFINITIONS

An adverse event (AE) is any untoward medical occurrence (e.g., sign, symptom, disease, syndrome, intercurrent illness, clinically significant abnormal laboratory finding, injury or accident) whether or not considered drug related. Any AE that emerges or worsens following administration of the informed consent and until the end of study participation will be collected. A pre-existing condition is one that is present prior to the start of the study and is to be reported as part of the subject's medical history unless it began as an AE in NI-AC301 or NI-AC302. Adverse events that began during NI-AC301 or NI-AC302 that are ongoing at the conclusion of either study will be reported as AEs at Baseline in this long-term safety study (NI-AC303) and followed. Prior conditions should be reported as an AE if the frequency, intensity, or the character of the condition worsens during the study or if the condition persists.

An adverse event or suspected adverse reaction is considered "unexpected" if it is not listed in the Investigator's Brochure or is not listed at the specificity or severity that has been observed.

A serious adverse event (SAE) includes any event, if in the view of either the investigator or the Medical Monitor results in any of the following outcomes:

- Death
- Life-threatening event (i.e., the subject was, in the opinion of the Investigator, at immediate risk of death from the event as it occurred. It does not apply to an AE that hypothetically might have caused death if it were more severe)
- Persistent or significant disability/incapacity (i.e., the AE results in a substantial disruption of the subject's ability to carry out normal life functions)
- Requires in-patient hospitalization or prolongs hospitalization (i.e., the AE required at least a 24-hour in-patient hospitalization or prolonged a hospitalization beyond the expected

length of stay; hospitalizations for elective medical/surgical procedures, scheduled treatments, or routine check-ups are not SAEs by this criterion)

- Congenital anomaly/birth defect (i.e., an adverse outcome in a child or fetus of a subject exposed to the molecule or investigational product before conception or during pregnancy)
- Does not meet any of the above serious criteria but may jeopardize the subject or may require medical or surgical intervention to prevent one of the outcomes listed above (i.e., is a significant or important medical event)

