7.5 SAFETY

7.5.1 ADVERSE EVENTS

All AEs that occur during the study or continue after enrollment into this study will be recorded and classified on the basis of MedDRA terminology. Treatment-emergent adverse events (TEAEs) are defined as AEs reported on or after the first day of enrollment in this long term safety study.

All information pertaining to an AE noted during the study will be listed by subject, detailing verbatim term given by the PI or designee, preferred term, system organ class (SOC), onset date, resolution date, severity, seriousness, action taken, outcome, and drug relatedness. The event onset will also be shown relative (in number of days) to date of first dose in this study.

Treatment-emergent AEs will be summarized by the number of subjects reporting a TEAE, SOC, preferred term, severity, relationship to study drug (causality), and seriousness. When summarizing AEs by severity and relationship, each subject will be counted only once within a system organ class or a preferred term by using the event with the highest severity and greatest relationship within each classification.

Adverse events will also be summarized by windows of exposure to study drug. The windows will include but are not limited to: 1) within the first 24 hours of exposure, 2) up to 1 month of exposure, 3) up to 3 months of exposure, 4) up to 6 months of exposure and 5) up to 12 months of exposure.

AEs will also be summarized based on extent of exposure as described in Section 7.7

Serious AEs will be summarized by severity, and relationship to study drug, and individual SAEs will be listed by subject. In addition, a list of subjects who prematurely discontinue from the study due to an AE will be provided.

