### 4.3 Baseline and Demographic Characteristics

Subject baseline and demographic characteristics, including age, race, ethnicity, and gender, will be summarized, as well as which previous Novan study the subject was enrolled in (NI-AC301 or NI-AC302) and previous treatment assignment (SB204 or Vehicle).

For female subjects the following summaries will be included: child-bearing potential, contraceptive use at baseline. Medical history will be summarized for each treatment group by SOC and PT and presented in listings. Adverse events ongoing at end of pivotal study will be carried forward to this study, will not be considered treatment-emergent for this study, and will be summarized separately by SOC, PT, and relatedness.

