Source: Listing xx.x.x.x, Program: xxxxx.sas, Output: T\_xx.x\_x\_xxxx.rtf, Generated on: DDMMMYYYY HH:MM

Protocol Number: NI-AC303

Using shell 14.3.2.1, Repeat table for the following:

Table 14.3.2.2 Shift from Baseline in Cutaneous Tolerability Evaluation - Scaling - Summarized Continuously by Study Visit Safety Population

Table 14.3.2.3 Shift from Baseline in Cutaneous Tolerability Evaluation - Dryness - Summarized Continuously by Study Visit Safety Population

Table 14.3.2.4 Shift from Baseline in Cutaneous Tolerability Evaluation - Pruritus - Summarized Continuously by Study Visit Safety Population

Table 14.3.2.5 Shift from Baseline in Cutaneous Tolerability Evaluation - Burning/Stinging - Summarized Continuously by Study Visit Safety Population

Protocol Number: NI-AC303

Table 14.3.3.1

Treatment Emergent Adverse Events (TEAE) Overview
Safety Population

Number of Subjects with	SB204 Experienced (N=XXX)	SB204 Naïve (N=XXX)	Overall (N=XXX)
Any TEAE	xx (xx.x)	xx (xx.x)	xx (xx.x)
Number of TEAEs	xx	xx	
Treatment-Related TEAE Number of Treatment-Related TEAEs	xx (xx.x)	xx (xx.x)	xx (xx.x)
	xx	xx	xx
TEAE Leading to Treatment Modification	xx (xx.x)	xx (xx.x)	xx (xx.x)
Number of TEAE Leading to Treatment Modification	xx	xx	xx
Treatment-Related TEAE Leading to Treatment Modification Number of TRTEAE Leading to Treatment Modification	xx (xx.x)	xx (xx.x)	xx (xx.x)
	xx	xx	xx
TEAE Leading to Treatment Discontinuation	xx (xx.x)	xx (xx.x)	xx (xx.x)
Number of TEAE Leading to Treatment Discontinuation	xx	xx	xx
Treatment-Related TEAE Leading to Treatment Discontinuation Number of TRTEAE Leading to Treatment Discontinuation	xx (xx.x)	xx (xx.x)	xx (xx.x)
	xx	xx	xx
Serious TEAE	xx (xx.x)	xx (xx.x)	xx (xx.x)
Number of Serious TEAEs	xx	xx	xx
Treatment-Related Serious TEAE	xx (xx.x)	xx (xx.x)	xx (xx.x)
Number of Treatment-Related Serious TEAEs	xx	xx	xx
TEAE Leading to Death	xx (xx.x)	xx (xx.x)	xx (xx.x)
Number of TEAE Leading to Death	xx	xx	xx
Treatment-Related TEAE Leading to Death	xx (xx.x)	xx (xx.x)	xx (xx.x)
Number of Treatment-Related TEAE Leading to Death	xx	xx	

Note: TEAE onset is based on the start of treatment in the LTS. Adverse events were coded using MedDRA 18.1. TR=Treatment-Related.

Source: Listing xx.x.x.x, Program: xxxxx.sas, Output: T\_xx.x\_x\_x\_x\_xxx.rtf, Generated on: DDMMMYYYY HH:MM

Protocol Number: NI-AC303

Table 14.3.3.2.1

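### AEs carried forward from the pivotal study can worsen on SB204 yet stay out of the TEAE tables, because no TEAE rule covers worsening

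*SAP*

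**What the plan says.** **Exclusion.** SAP 4.5.1: "Adverse events ongoing at end of the pivotal study will be carried forward to this study, will not be considered treatment-emergent for this study". Such events get a separate summary by system organ class, preferred term and relatedness. SAP 4.3 has the same rule: "Adverse events ongoing at end of pivotal study will be carried forward to this study, will not be considered treatment-emergent for this study". Neither section mentions worsening.

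**Definition of a TEAE.** SAP 4.5.1: "Treatment-emergent AEs (TEAEs) will be defined as AEs reported on or after the first day of enrollment in this long term safety study". Protocol 7.5.1 matches it: "Treatment-emergent adverse events (TEAEs) are defined as AEs reported on or after the first day of enrollment in this long term safety study". The protocol synopsis (Statistical Methods, Adverse Events) selects reported AEs by whether they occurred on or after the Baseline date. The notes to SAP Tables 14.3.3.1, 14.3.3.2.2 and 14.3.3.13 and to Listing 16.2.8.1 use a different reference point: "TEAE onset is based on the start of treatment in the LTS".

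**Collection.** Protocol 6.1: "Any AE that emerges or worsens following administration of the informed consent and until the end of study participation will be collected". The same section says a prior condition is to be reported as an AE if its frequency, intensity or character worsens. Under Protocol 4.3, AEs from NI-AC301 or NI-AC302 that are still ongoing "will be reported as AEs at Baseline in this long-term safety study (NI-AC303) and followed".

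**The concern.** Worsening is collected, but no analysis rule picks it up. The exclusion depends only on whether the event was open at the end of the pivotal study, not on what it did afterwards.

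This matters most for the SB204 Naïve group of SAP 3.5.1, who had vehicle in the pivotal study and first receive active drug here. An event that began on vehicle and worsened on first SB204 exposure bears directly on the primary safety objective. The same applies to a carried-forward event of any origin that becomes serious or ends treatment.

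The tables at stake are the main AE output: the overview, the system organ class and preferred term tables, and the related, modification, discontinuation, serious, death and severity tables. The shells restrict all of them to TEAEs.

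**Working it through.** The documents give no figure to reproduce. The check is to trace one event through the text, then bound the size under stated assumptions.

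**Step 1: the event.** Suppose a mild AE starts on vehicle in the pivotal study, is ongoing at Week 12, does not warrant stopping drug (so Exclusion 3 in Protocol 3.7.3 does not apply), and becomes severe after the first SB204 dose in the LTS. There are two ways to record it:

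| | (a) Carried-forward record updated | (b) New AE record opened |
|---|---|---|
| Onset date | In the pivotal study | In the LTS |
| SAP 4.3 and 4.5.1 exclusion | Applies | Does not apply: this record was not open at the end of the pivotal study |
| Shell rule (onset from start of LTS treatment) | Fails | Met |
| TEAE tables 14.3.3.1 to 14.3.3.14 | Absent | Present |
| Listings 16.2.8.2 to 16.2.8.5 (all titled treatment-emergent) | Absent | Present where the criterion is met |
| Table 14.1.4 | Present, without severity, relatedness or worsening | Original entry present |
| Listing 16.2.8.1 (all AEs) | Present, not flagged as a TEAE | Present, flagged as a TEAE |

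**Step 2: which route do the documents choose?** Neither is stated. Reporting carried-forward AEs at Baseline and then following them (Protocol 4.3 and 6.1) leans towards one continuing record, route (a). The sentence on worsened prior conditions in Protocol 6.1 leans towards route (b), but it does not say whether it covers an event already on file as an AE, or whether it calls for a new onset date. Listing 16.2.8.1 has one severity and one start date per row, which fits either route.

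**Step 3: the TEAE wordings side by side.**

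| Source | Criterion | Carried-forward AE that keeps its pivotal-study onset |
|---|---|---|
| Protocol 7.5.1 | Reported on or after enrolment | Literally in, since it is reported at Baseline |
| Protocol synopsis | Occurred on or after the Baseline date | Out |
| SAP 4.5.1 | Reported on or after enrolment, with a carve-out for ongoing AEs | Out |
| Shell notes | Onset from start of LTS treatment | Out |

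None of the four mentions worsening.

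**Step 4: size.** The planned number is about 600 (Protocol 7.9, SAP 3.1). The documents give no rate of ongoing AEs at entry or of later worsening, so both ranges below are assumptions.

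- Subjects with an ongoing AE at entry, assumed 5-20%: 600 × 0.05 = 30 to 600 × 0.20 = 120.
- Of those, subjects whose event worsens, assumed 5-20%: 30 × 0.05 = 1.5 to 120 × 0.20 = 24.
- As a share of 600: 1.5/600 = 0.25% to 24/600 = 4.0%.

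Overall TEAE incidence counts each subject once, so an affected subject with any other TEAE stays in the numerator. For given rates, 0.25-4 percentage points is therefore an upper bound, reached only if every worsening takes route (a) and no affected subject has another TEAE.

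**The case against.** The strongest reply is that the SAP is read together with the protocol. Protocol 6.1 asks for worsened conditions to be reported as AEs. A worsening reported that way during the LTS meets the SAP's own TEAE definition and reaches every relevant table. That route is open, and whether grades are overwritten depends on data-entry rules that these documents do not contain. A reader might infer that carried-forward AEs can never be treatment-emergent and drop out of every TEAE table. The documents do not support that, because it holds only under route (a). What remains is that the route which avoids the problem is not secured anywhere, while the exclusion is explicit and stated twice.

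A reader might also infer from the word *reported* that the protocol makes every carried-forward AE a TEAE, so that protocol and SAP differ by the whole group with ongoing events. That is only a literal reading of Protocol 7.5.1. The synopsis goes by occurrence, Protocol 7.1 leaves detailed methodology to the SAP, and the SAP carve-out can be taken as settling the matter. The wording still needs aligning. The shell reference to start of treatment is a smaller matter, since drug is dispensed at the Baseline visit and the dates should usually be close.

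There are partial safeguards:

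- Listing 16.2.8.1 shows every AE with severity, relationship, action taken and seriousness, but it is not a summary.
- Table 14.1.1.1 counts AE discontinuations without regard to TEAE status, but names no event.
- The text of SAP 4.5.1 promises SAE listings and a discontinuation list for AEs generally, but the shells narrow both to TEAEs.
- The tolerability shift tables track five facial signs regardless of TEAE status. They do not cover headache, a theoretical risk named in Protocol 1.5, or reactions on the chest, back and shoulders, which SAP 4.4 indicates were untreated in the pivotal studies. They are also not split by prior treatment.
- Exclusion 3 shrinks the pool of ongoing AEs but does not empty it.
- SAE reporting under Protocol 6.3 does not depend on TEAE status.

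**Conclusion.** The point holds in conditional form. SAP 4.3 and 4.5.1 exclude AEs ongoing at the end of the pivotal study without qualification, and no TEAE definition covers worsening. If worsening is recorded on the existing entry, events that become worse, serious or treatment-ending on SB204 can be lost from the TEAE tables and from Listings 16.2.8.2 to 16.2.8.5. Under that route the omission can only lower the counts. If worsening opens a new record, nothing is lost.

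The documents do not allow the size to be derived. The 2-24 subjects rest wholly on the assumed 5-20% rates, and the percentage-point range is a ceiling, not an estimate of the effect. The split between experienced and naïve subjects is not given, so no group-specific number of subjects can be stated. The likely effect on overall incidence is small. The case for correction is that a few worsened or serious events are what a long-term safety study is meant to find. This should be corrected before database lock.

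**What to change.** 1. Use one rule in Protocol 7.5.1, SAP 4.3 and 4.5.1 and the shell notes: a TEAE is an AE with onset on or after the first LTS dose, or an AE ongoing at entry that increases in severity or becomes serious on or after that dose, dated at the worsening. Define it by onset or worsening date, not by when the event was reported. Align the synopsis wording.
2. State how worsening of a carried-forward AE is recorded: as a new record, or on the existing record with a worsening flag and date.
3. Keep carried-forward AEs that do not worsen in Table 14.1.4. Add the relatedness that SAP 4.3 and 4.5.1 already promise, plus severity.
4. Let the SAE and discontinuation listings cover all AEs, as the text of SAP 4.5.1 reads, with a TEAE flag. A carried-forward event that ends treatment without a change in grade is then still shown.

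The cost is one SAP sentence, one extra derivation, aligned footnotes, a data-entry instruction and a wording change to the protocol. TEAE incidence may rise slightly.

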	Subjects will be assessed at each visit through Week 40 for cutaneous tolerability on the face. Tolerability will be assessed on a scale of 0 to 3 where 0=none, 1=mild, 2=moderate, and 3=severe for erythema, scaling, dryness, pruritus, and burning/stinging. The body surface area (BSA) treated (based on locations) will be collected at each visit for each subject Extent of exposure will be calculated for each subject based on the number of treatments and treatment area. Extent of exposure will also be summarized on a unit day which will be defined as total exposure divided by the total number of days enrolled.
Endpoints	Safety endpoints will include adverse events, changes in physical
	examination and changes in vital sign measurements. Any clinically significant changes noted during the physical exam as well as from the vital sign measurements will be recorded as adverse events and included in the comparison. Urine pregnancy tests in women of child-bearing potential will be conducted at each visit.
	Tolerability endpoints will include the investigator's assessment of erythema, scaling, dryness, and the subject's report of pruritus and burning/stinging based on the preceding 24 hours.
Statistical Methods	All statistical processing will be performed using statistical analysis software (SAS®) unless otherwise stated. Safety analyses will be performed using the safety population.
	Safety Analyses
	Adverse Events
	All AEs occurring during the study will be recorded and classified on the basis of the Medical Dictionary for Regulatory Authorities (MedDRA) terminology. Descriptions of AEs will include the date of onset, the date the AE ended, the severity of the AE, the relationship to study medication, and the outcome. All reported AEs that occurred on or after the Baseline date will be included in the summaries and analysis. Summaries will be presented to describe the characteristics of the adverse events reported and will include the number and percentage of subjects who report at least one AE and the number of events reported by severity, seriousness, and relationship to study medication. A
	summary of adverse event system organ class (SOC) and preferred terms (PTs) will also be presented. A subject will be counted only once under

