3. STUDY DESIGN

Figure 1 depicts the overall study design for this 40-week, open label study in subjects with acne vulgaris dosed once daily with SB204 4%. Subjects must have completed participation in one of the pivotal acne trials (NI-AC301 or NI-AC302) to be eligible to participate in this long term safety trial. Subjects will be treated chronically or repeatedly as recommended by the Investigator for up to 40 weeks. The Investigator may stop treatment if the subject's acne is in remission and re-initiate treatment if the subject's acne recurs. Any subject who is determined to be clear will remain enrolled in the study until study completion or termination. The total time on study will be counted as the days from enrollment until the subject discontinues or the study terminates.

Figure 1: Study Diagram

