### 4.4 Extent and Duration of Exposure

Summaries of the duration of exposure, days of exposure, and extent of exposure (calculated total grams) to study drug will be presented, overall and by whether previously randomized to SB204 (SB204 experienced) or randomized to Vehicle (SB204 naïve). This information plus study drug management details will be listed as well. All exposure endpoints will take into account whether the subject received SB204 in the previous study (NI-AC301 or NI-AC302).

Duration of exposure will be defined as:

Date of Last Drug Administration – Date of First Drug Administration + 1 day

Where date of first drug administration is the date of first treatment in the previous pivotal study for subjects randomized to SB204 in the previous study, and date of first dose in the LTS for subjects randomized to vehicle in the previous study.

Days of exposure will be defined as the total number of days that the subject reported taking study medication, and includes the days of exposure to SB204 in the previous study (NI-AC301 or NI-AC302) if applicable.

Extent of exposure will be based on the number of areas treated (face, upper back, and/or upper chest/shoulders, and any other areas reported) and the number of days with treatment. For subjects randomized to SB204 in the previous studies, drug was only applied to the face so for the days of exposure from the previous studies, it will be assumed that there is only one area of application, i.e. the face.

Each application is equal to 0.9 g. Extent of exposure is estimated as the sum of application areas (face only=1, face and chest=2, etc.) times the number of days of application to those areas times 0.9g. For example, a subject who applies 200 applications to the face only will have extent of exposure = 180g, while a subject who applies 100 applications to the face and 50 applications to the upper back will have extent of exposure = 135 g. The maximum extent of exposure would be: [0.9 grams x number of days on treatment in previous study] + [0.9 grams x 4 areas x number of LTS days on treatment]. Most subjects will have less exposure than this, so extent of exposure will be categorized logically depending on actual distribution of subjects. Initially, quartiles will considered.

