Number of Subjects with Exposure	xx	XX	XX
Mean (SD)	xx.x (xx.xx)	xx.x (xx.xx)	xx.x (xx.xx)
Median	XX.X	XX.X	XX.X
Min, Max	X.X, XX.X	X.X, XX.X	x.x, xx.x
Unknown	,	,	•
Days of Exposure			
n	xx	xx	XX
Mean (SD)	xx.x (xx.xx)	xx.x (xx.xx)	xx.x (xx.xx)
Median	XX.X	XX.X	XX.X
Min, Max	x.x, xx.x	x.x, xx.x	X.X, XX.X
Unknown			
Areas of Application			
Face	xx (xx.x)	xx (xx.x)	xx (xx.x)
Upper Back	xx (xx.x)	xx (xx.x)	xx (xx.x)
Upper Chest	xx (xx.x)	xx (xx.x)	xx (xx.x)
Shoulders	xx (xx.x)	xx (xx.x)	xx (xx.x)
Other	xx (xx.x)	xx (xx.x)	xx (xx.x)
Extent of Exposure (grams)			
Mean (SD)	xx.x (xx.xx)	xx.x (xx.xx)	xx.x (xx.xx)
Median	XX.X	XX.X	XX.X
Min, Max	x.x, xx.x	x.x, xx.x	x.x, xx.x
Unknown	xx (xx.x)	xx (xx.x)	xx (xx.x)
1-100 grams	xx (xx.x)	xx (xx.x)	xx (xx.x)
>100-330 grams	xx (xx.x)	xx (xx.x)	xx (xx.x)
>330-675 grams	xx (xx.x)	xx (xx.x)	xx (xx.x)
>675 grams	xx (xx.x)	xx (xx.x)	xx (xx.x)

Notes: All exposure endpoints includes exposure to SB204 from the previous study (NI-AC301 or NI-AC302), if applicable. Duration of Exposure = Date of Last Drug Administration - Date of First Drug Administration + 1 day. Days of exposure will be defined as the total number of days that the subject reported taking study medication. Areas of application indicate if the subject ever applied drug to that area. Each subject is counted only once per area.

Extent of exposure is determined as: 0.9 grams times the number of application areas times the number of days applied. Application to neck and jawline are considered part of application to the face when determining extent of exposure. Source: Listing xx.x.x.x.x, Program: xxxxx.sas, Output: T xx.x x x xxxx.rtf, Generated on: DDMMMYYYY HH:MM

Protocol Number: NI-AC303

Table 14.2.2.1
Inflammatory Lesion Counts by Study Visit (Face Only)
Safety Population

		SB204 (N=XXX)		
		Count	Absolute Change	Percent Change
Visit	Statistic		from Baseline	from Baseline
Baseline	N	XX		
	Mean	XX.X		
	SD	XX,XX		
	Median	XX		
	Min. to Max.	XX to XX		
Week 4	N	XX	XX	XX
	Mean	XX.X	XX.X	XX.X
	SD	XX, XX	XX,XX	XX,XX
	Median	XX	XX,X	XX,X
	Min. to Max.	XX to XX	XX to XX	XX to XX
Week 12	N	XX	XX	XX
	Mean	XX.X	XX.X	XX.X
	SD	XX,XX	XX,XX	XX,XX
	Median	XX	XX,X	XX,X
	Min. to Max.	XX to XX	XX to XX	XX to XX

Source: Listing xx.x.x.x, Program: xxxxx.sas, Output: T xx.x x x xxxx.rtf, Generated on: DDMMMYYYY HH:MM

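### The AE-by-duration tables count planned off-drug time before a restart as exposure, and give no window rule for events after a final stop

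*SAP*

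**What the plan says.** Protocol Section 3 builds interruptions into the regimen: "The Investigator may stop treatment if the subject's acne is in remission and re-initiate treatment if the subject's acne recurs". It also says: "Any subject who is determined to be clear will remain enrolled in the study until study completion or termination". Adverse events are collected until the final visit (Protocol 4.3.1), whether or not the subject is applying drug.

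SAP 4.4 defines two time measures:

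- Duration of exposure: "Date of Last Drug Administration – Date of First Drug Administration + 1 day". Nothing is subtracted for interruptions. For subjects given SB204 in the pivotal study (experienced), the first date is in that study. For subjects given vehicle (naïve), it is in the long-term study.
- Days of exposure: "Days of exposure will be defined as the total number of days that the subject reported taking study medication". The note to Listing 16.2.6 confirms that this is duration less the days not taken.

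For the signal analysis, SAP 4.5.1 uses the first measure: "Adverse events will also be summarized by windows of duration of exposure to study drug". The windows are day 1, 2-30, 31-90, 91-180 and 181-365. The note to Table 14.3.3.2.1 starts the clock at the first SB204 dose, although SAP 4.5.1 describes the first window as Day 1 of the long-term study. Neither clock removes interruptions. Treatment-emergent events are those reported on or after the first day of enrollment. There is no upper limit relative to the last application and no on-drug or off-drug flag. The N for each window is not defined.

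**The concern.** The windowed tables exist to show whether harm depends on how long the drug has been used. Long-term safety is the primary objective and there is no control arm, so few other analyses could show this. If the axis includes weeks or months without drug, an event can appear in a late exposure window although the subject has had much less drug than the column label implies. An event during a pause is tabulated in an exposure window with nothing to mark it as off drug. Days of exposure, which would separate these cases, appears in Table 14.2.1 and Listing 16.2.6 but in no AE table.

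**Working it through.** **Inputs from the documents.** The two definitions in SAP 4.4, the windows in SAP 4.5.1, a maximum of 280 treatment days (Protocol 2.1), and 12 weeks (84 days) in the pivotal study.

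**Assumptions.** One pause of the stated length, every other day dosed, last dose on study day 280, and each event placed by its onset day on the clock. The documents give neither the frequency nor the length of interruptions.

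**Plan's own figures.** None bears directly on this point. The worked examples in SAP 4.4 reproduce: 200 × 0.9 = 180 g and (100 + 50) × 0.9 = 135 g. They confirm that grams count application days only.

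**Step 1. Duration against drug-days, naïve subject.** Duration = 280 − 1 + 1 = 280 in each row. Drug-days = 280 − days off.

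| Pause (study days) | Days off | Drug-days | Share of duration off drug | Off-drug days in 91-180 | Off-drug days in 181-280 |
|---|---|---|---|---|---|
| 85-112 | 28 | 252 | 10% | 22 of 90 (24%) | 0 of 100 |
| 85-168 | 84 | 196 | 30% | 78 of 90 (87%) | 0 of 100 |
| 85-252 | 168 | 112 | 60% | 90 of 90 (100%) | 72 of 100 |

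**Step 2. Where events land, pause on days 85-168.** After the pause, drug-days at onset = onset day − 84.

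| Onset day | Status | Window by duration | Drug-days at onset | Window by drug-days |
|---|---|---|---|---|
| 150 | off drug | 91-180 | 84 | 31-90 |
| 200 | on drug | 181-365 | 116 | 91-180 |
| 250 | on drug | 181-365 | 166 | 91-180 |
| 270 | on drug | 181-365 | 186 | 181-365 |

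**Step 3. Same pause, experienced subject, no gap between studies.** The clock is 84 days ahead, so the pause covers clock days 169-252. Duration is 84 + 280 = 364, drug-days are 364 − 84 = 280, and 84/364 = 23% is off drug. Only 12 days of the pause (169-180) fall in the 91-180 window. An event on study day 200 is on clock day 284 with 200 drug-days, and stays in 181-365 either way. An event on study day 150 is on clock day 234 with 168 drug-days, and moves from 181-365 to 91-180. The effect therefore differs between the two groups.

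**Step 4. Final stop without restart.** Suppose a naïve subject takes the last dose on day 84, stays enrolled, and has an event on day 200. Duration of exposure is 84 days and time since first dose is 200 days. The event is treatment-emergent, but the SAP does not say whether it belongs in 31-90, in 181-365 or in no window.

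**Step 5. Direction.** If a share f of a window's N is off drug throughout it, observed incidence = (1 − f) × p_on + f × p_off. With assumed p_on = 5% and p_off = 2%, f = 10%, 25% and 50% give 4.7%, 4.25% and 3.5%, so the excess of on-drug over off-drug incidence shrinks by the factor (1 − f). Two effects work the other way. Background events during pauses are credited to exposure. And if N is the whole safety population, re-windowing moves the day 200 and day 250 events out of 181-365 with no change in N, so the duration table shows more late events than a drug-day table would.

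**Step 6. Whether grams fill the gap.** 100 days on two areas gives 100 × 2 × 0.9 = 180 g, the same as 200 days on the face alone. The gram categories cannot separate the two.

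**The case against.** Treatment as needed is the planned regimen, and time since first dose is a legitimate axis for its safety. A lag rule for off-drug events could mislabel delayed reactions, and counting every event to the last visit is conservative for overall incidence. These points stand, and are reasons to keep the existing table.

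The plan also contains mitigation. Days of exposure sits beside duration in Table 14.2.1. AEs are tabulated by grams, which exclude off-drug days, and Protocol 7.7 gives the extent-of-exposure analysis the task of finding a duration or area signal. The AE listing prints duration and extent for each event. This helps, but grams mix days with number of areas (Step 6), so no AE table isolates time on drug.

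Dated applications are not documented. Listing 16.2.6 works from a count of missed days per visit interval, so drug-days at onset will sometimes be imprecise.

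A reader might also infer more than the documents support:

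- **That the error favours the drug.** Step 5 shows effects in both directions. The sign depends on N and on the off-drug event rate, and neither is given.
- **That a large share of exposure is drug-free.** The 60% case needs a 168-day pause, a restart and dosing to day 280. Without a restart, duration ends at the last dose.
- **That restoring the synopsis summary would reveal intermittent use.** That summary is "total exposure divided by the total number of days enrolled". One area daily for 280 days gives 0.9 × 280/280 = 0.90 g per day. Three areas on 93 of 280 days gives 2.7 × 93/280 = 0.90 g per day. Protocol 3.1.3 and 7.7 do not carry it either.
- **That subjects with at least 360 dosing days should be counted in both groups.** Naïve subjects can reach only 280. Experienced subjects would need 360/364, about 99% of possible days.

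**Conclusion.** The point holds as a limitation of the duration-window tables. Off-drug time before a restart is counted as exposure, and events after a final stop have no window rule. Individual events can be placed one window or more too late relative to drug received, which can blur a duration-related signal.

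The placement follows directly from the SAP's definitions, read with onset day as the placing rule. The figures for single subjects are illustrations with assumed pauses. No trial-level size or direction can be stated, because interruption rates are not given and the window N is undefined. It is a cheap improvement to a stated signal analysis. It does not invalidate the AE summaries as a whole.

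**What to change.** - Keep Table 14.3.3.2.1 and its repeats, label the axis as time since first SB204 dose, and state one starting point for the clock.
- Add a companion version windowed by cumulative days of exposure up to AE onset. Use the diaries and the start and stop dates named in SAP 2.3, at visit-interval precision where dates are lacking, with the existing unknown category.
- Define N for each window as the subjects who reach that window on the axis in use.
- Flag each treatment-emergent event as on drug or off drug at onset, using a lag after last application fixed in advance, and tabulate both. State where events after a final stop are placed.
- Report the number of subjects by actual dosing days, for naïve and experienced separately, with cut-offs that each group can attain (for example at least 180).

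No new visits or assessments are needed. The cost is modest extra programming and some subjects or events classed as unknown. For experienced subjects, pivotal-study dosing data are also needed, but SAP 4.4 already uses those for days of exposure.
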